Our long-term goal is to implement cost-effective treatments that reduce the morbidity and mortality associated with alcohol and substance misuse. VA has widely implemented evidence-based cognitive-behavioral therapy (CBT) for treatment of substance abuse disorders (Karlin & Cross, 2014). The primary goal of the current study is to evaluate the clinical effectiveness and cost effectiveness of CM as an adjunct to CBT for AUD. The trial will also explore the potential utility of a long-term abstinence incentive on treatment utilization and alcohol outcomes. We plan to conduct a comparative effectiveness trial with a 2 x 2 factorial design in which 140 veterans with AUD will be proactively recruited and randomized to receive either CM as an adjunct to state-of-the-art evidence-based CBT, or receive CBT alone; and to one of two long-term incentive conditions (i.e., receipt of a monetary incentive for abstinence/low-risk drinking at 6-months vs. no incentive). Specific aims include:

AIM 1: To evaluate the effectiveness of mobile contingency management, as an augment to evidence-based CBT for AUD, on (1) treatment engagement and retention, and (2) reduction in heavy drinking days and abstinence from alcohol at post-treatment, 6-month and 12-month follow-ups.

Hypothesis 1a: Mobile contingency management for AUD will be associated with greater treatment engagement and treatment completion.

Hypothesis 1b: Mobile contingency management for AUD will be associated with decreased self-reported heavy drinking days and increased rates of abstinence from alcohol at each follow-up.

AIM 2: To evaluate the cost effectiveness of CM as an adjunct to evidence-based CBT for SUD in quality adjusted life years (QALY).

Hypothesis 2: CM paired with CBT will result in greater cost-effectiveness compared to the CBT alone as measured by the incremental cost-effectiveness ratio.

AIM 3: To explore the effects of a long-term (six-month) abstinence incentive on (1) treatment utilization and (2) alcohol outcomes at the 6-month and 12-month follow-ups.

Hypothesis 3: A long-term abstinence incentive will (1) increase utilization of AUD aftercare and (2) be associated with reduced heavy drinking days and increased abstinence rates.

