D.8.1. Diagnostic Assessment and Psychiatric Symptom Measures. We will assess AUD and other major psychiatric disorders with the Structured Clinical Interview for DSM-5 (SCID-5). Our group has trained diagnostic interviewers for our studies using training videos, observation of live interviews, and monthly meetings to prevent rater drift. Inter-rater reliability across previous interviewers has been excellent (kappa = .96). We will administer the Clinical Institute Withdrawal Assessment to assess past alcohol withdrawal symptoms. Due to the high comorbidity with AUD, we will measure severity of PTSD symptoms with the PTSD Checklist-5 and measure depressive symptoms with the Patient Health Questionnaire-9. At each session, participants will be asked four questions regarding suicidality. The items will be used to examine how the co-occurring mental health problem of suicidal thoughts and behaviors impacts the progression of AUD treatment, as well as the extent to which this treatment simultaneously reduces alcohol use and the occurrence of suicide-related phenomena.

D.8.2. Alcohol-related Measures. Standard self-report and interview-based alcohol-related assessment measures (e.g., severity, craving, consequences; see Table 2) will be used to measure alcohol-related behaviors, perceptions, and attitudes. The Alcohol Purchase Task will be used to provide a behavioral economic measure of the relative reinforcing efficacy of alcohol (Kiselica, Webber, & Bornovalova, 2016).

D.8.3. Self-Efficacy Measures. Attitudes toward behavior change with respect to alcohol will be measured with Alcohol Abstinence Self-Efficacy scale which has demonstrated reliability and validity. Additionally, the Alcohol Readiness to Change will assess motivation to quit alcohol.

Table 3. Measures Administered at Major Study Time Points

Measure	Completer	Time				
		Screen	Txt Session	Post-txt	6-mo. f/u	12-mo. f/u
Diagnostic Assessment						
SCID-5	Study staff	X				
Clinical Institute Withdrawal Assessment	Study staff	X				
Psychiatric Symptom Measures						
PTSD Checklist-5	Participant	X		X	X	X
Patient Health Questionnaire	Participant	X		X	X	X
Suicidality Questions	Study staff	X	X	X	X	X
Alcohol-Related Measures						
AUDIT	Participant	X		X	X	X
BAM	Participant	X		X	X	X
BAM -C	Participant		X			
Penn Craving	Participant	X		X	X	X
Drinker Inventory of Consequences	Participant	X		X	X	X
Alcohol Abstinence Self-Efficacy	Participant	X		X	X	X
NIAAA Alcohol Use Frequency	Participant	X				

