D.8.5. Temporary Measures During COVID-19 Pandemic. Given that media outlets are reporting increased rates of alcohol use during COVID19 pandemic, and there is a high incidence of PTSD among the veterans who are enrolled in this study, we would like to ask participants to complete measures related to stress, trauma, and coping strategies during the pandemic. New participants will complete these measures at their first visit, and ongoing participants will complete them at their next study visit. We are adding the CAIR Pandemic Impact Questionnaire (Lang, 2020; https://www.nlm.nih.gov/dr2/CAIR-PIQ_scoring.pdf), and another measure, COVID Core Questions, with variables of interest. If a participant endorses any item marked with an asterisk on the COVID Core Questions measure, we will ask them to complete a PTSD Checklist 5 related to that specific event..

D.8.6. Treatment Process Measures. Protocol adherence will be defined as completing the baseline assessment, post-treatment assessment, and follow-ups at 6, and 12 months. Process measures will include the proportion of abstinence videos uploaded (intervention), the number of counseling sessions completed. We will measure patient satisfaction with questionnaires related to this study's treatment aims and to satisfaction with treatment components. During the one-week follow-up visit, we will perform qualitative interviews with participants to gain information from the participant about his/her/their user experience with the CBT protocol and mobile phone contingency management app. The qualitative interview will be recorded for qualitative analyses.

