D.8.9. Quality of Life and Health Care Utilization. VA administrative data will be accessed via the VA Corporate Data Warehouse to provide objective measures of VA health care utilization. Our team has extensive experience accessing and utilizing VA data (Elhai, [name], & Ford, 2008; [name], Bosworth, Grambow, Dudley, & [name], 2002; [name], Bosworth, Stechuchak, Strauss, & Butterfield, 2006). Additionally, we will collect self-reported use of non-VA healthcare and 12-step programs and information about insurance coverage. Health care related quality of life will be assessed with the EuroQol (United Kingdom Alcohol Treatment Trial Team, 2005) at baseline and each of the follow-ups.

D.9. Participant Reimbursement

Participants will be paid as follows:

Project Milestone	Amount
Screening visit	\$50
CM abstinence reinforcement	\$611
End-of-treatment visit	\$50
6-month follow-up	\$100
Bioverified abstinence at 6 month follow-up (if randomized to long-term incentive condition)	\$300
12-month follow-up	\$125
TOTAL	\$1236

D.10. Potential Challenges and Solutions

One potential challenge to the success of this project is recruitment and retention. Previous AUD trials in veterans indicate lost-to-follow-up rates near 30% at 12 month follow-up (Hagedorn et al., 2013). We have implemented several methods to increase retention in our trials (e.g., pre-alert letters, birthday cards, reminder

calls, thank you notes) and have obtained excellent retention rates ($>80\%$ at 12-months) in substance using populations (e.g., homeless veterans). We will use these methods and have budgeted to provide an incentive to participants to complete each follow-up. Missing data will be treated as indicative of relapse/heavy drinking. Our pilot data and experience in previous trials indicate that proactive recruitment of veterans with AUD is feasible. To augment our proactive recruitment method, we could include reactive recruitment strategies and include referrals from the SUD clinic at DVHCS. Another potential concern is lost/stolen study equipment. We now have extensive experience with providing veterans with a smartphone and monitoring devices to perform mobile monitoring for CM (e.g., R34AA023877; R01CA196304; 1I01HX001109; 1I01RX001301) and have budgeted for anticipated lost/stolen equipment. Costs of lost equipment will be captured and included in cost analyses.

E. DATA AND SAFETY MONITORING

E.1. Risk/Benefit Ratio

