E.1.3. Psychiatric Emergencies. As this study includes a novel therapeutic intervention that is behavioral in nature, we do not anticipate study-related SAEs to occur. It is not unanticipated that participants may endorse suicidal or homicidal ideation. We have developed a homicidal (HI) and suicidal (SI) risk assessment checklist based on the currently available research evidence base. All staff members are trained in the use of the assessment instrument, and attend monthly supervision meetings in which HI/SI assessments are regularly reviewed. Our laboratory has a policy regarding SI and HI risk assessment and follow-up. According to the policy, if a participant is deemed at "high" risk of suicide or homicide, the study staff providing the assessment will contact a senior staff member with clinical training who will provide a second opinion. If the senior staff member determines that the participant is in imminent risk of suicide or homicide, that participant will be escorted to the DUMC or DVAHCS emergency room for evaluation for psychiatric hospitalization. If at any time a participant is deemed by our staff to be at imminent risk of harm to self or others, he/she will be immediately withdrawn from the study upon being escorted to the emergency room. If a participant is deemed to be at "low" or "moderate" risk, the study staff member performing the assessment will discuss treatment options with the participant and discuss psychiatric emergency resources that may be available to him or her. Finally, in the case

of moderate SI or HI, study staff will review the assessment with a senior staff member in order to ensure that follow-up has been adequate.

E.1.4. Participant Referrals. Following the standard of care for AUDs, all participants will be referred to aftercare and encouraged to participate in 12-step programs or outpatient relapse prevention treatment in the Durham VA Health Care System or at DUMC following completion of the 12-session CBT intervention. In addition, appropriate referrals will be completed to address any clinically significant increases in symptoms of comorbid psychiatric or medical problems. Referrals will be made first to treatment at DVAHCS, where participants must be enrolled for primary care services. In the event that treatment is not available at DVAHCS or DUMC, referral will be made to a community provider.

E.2. Data and Safety Monitoring Plan

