We plan to ask participants to report both gender and biological sex so that we can evaluate the role of biological sex on study outcomes. The association between sex and outcomes will be evaluated for all three aims. We will conduct sensitivity analyses to determine how variability in demographic/baseline variables influence estimates of treatment effects by analyzing and reporting the effects of randomization on males and females separately.

Multilevel modeling (MLM) will be used to analyze primary treatment outcomes (i.e., number of heavy drinking days; abstinence outcomes). MLM is appropriate for analyzing repeated-measures data; however, unlike ANOVA, MLM can accommodate data missing at random (Searle, Casella, & McCulloch, 1992). Because MLM takes into account the shared variance among observations within a given person, it can be used to leverage repeated measurements of alcohol use to enhance statistical power.

Although we do not anticipate much missing baseline data, we do anticipate missing values at post-treatment and each of the 6- and 12-month follow-ups due to attrition. Given evidence that maximum likelihood (ML) and multiple imputation (MI) provide the least biased results in comparison to last observation carried forward and worst-case scenario (i.e., missing=relapsed) in alcohol clinical trials under varying missing data assumptions (Hallgren & Witkiewitz, 2013), both approaches will be used here. MLM uses ML estimation; thus, missing values result in casewise—but not listwise—deletion. Consequently, participants with missing data will still be included in the analyses; estimates based on them will simply have a greater level of uncertainty. MI will be used to impute missing data using baseline demographic, clinical, and drinking measures. Regression parameter estimates will be computed for each imputation dataset and then pooled using Rubin's rules (Rubin, 1976). Sensitivity analyses will be conducted to determine how modeled treatment effects may vary by missing-data approach.

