Aim 1: To examine the first hypothesis that CM will be associated with greater treatment engagement and treatment completion than the control condition, treatment engagement will be defined as the number of counseling sessions completed, with treatment completion defined as completion of all 12 counseling sessions. Potential group differences in treatment engagement as a function of counseling sessions completed will be examined using independent *t*-tests. Contingency-table analysis will be used to examine whether a greater proportion of the CM participants complete the treatment in comparison to the control group. The second hypothesis is that CM will be associated with higher rates of self-reported abstinence and fewer heavy drinking days at 6 and 12 months. MLM will be used to model each of these outcomes. Specifically, logistic MLM will be

conducted to model abstinence as a function of treatment, time (categorized as end of treatment, 6 months, 12 months), and the interaction between treatment and time. Randomization to long-term abstinence incentive will be covaried. Linear contrasts will be specified at each time point to examine the hypothesis that CM will result in higher abstinence rates than CBT alone at 6 and 12 months. A similar count-based model (e.g., Poisson, negative binomial) will be conducted to analyze number of days of heavy drinking (per 30 days). In addition to modeling the effects of treatment, time, and the interaction between treatment and time, number of days of heavy drinking recorded at baseline and randomization to the long-term abstinence incentive will be covaried. Again, linear contrasts will be derived at each time point to compare treatment effects at 6 and 12 months.

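### As written, a participant judged at imminent risk is withdrawn from the study rather than from treatment only, so later visit-based outcomes would not be collected

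*Combined protocol and SAP*

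**What the plan says.** The rule is in E.1.3 (Psychiatric Emergencies). A participant rated at high risk of suicide or homicide is referred upward: "the study staff providing the assessment will contact a senior staff member with clinical training who will provide a second opinion". If the senior colleague finds imminent risk, the person is taken to the emergency room. The section then adds, for a finding of imminent risk at any time, that "he/she will be immediately withdrawn from the study upon being escorted to the emergency room". People at low or moderate risk stay in.

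Four other parts of the plan bear on what this rule removes.

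- **Assessments.** D.8 makes the follow-ups in-person. D.1 sets the primary endpoint as heavy drinking days in the past 30 days at 6 months. Under D.8.9, "Health care related quality of life will be assessed with the EuroQol" at baseline and each follow-up. Aim 2 in section F bases QALY change on drinking status at 12 months.
- **When risk is assessed.** D.8.1 states: "At each session, participants will be asked four questions regarding suicidality". Table 3 adds screening, post-treatment, 6 months and 12 months.
- **Missing data.** Section F attributes missing follow-up values to attrition. It uses maximum likelihood (ML) through the multilevel model, and also multiple imputation (MI): "MI will be used to impute missing data using baseline demographic, clinical, and drinking measures". It promises sensitivity analyses across missing-data approaches. D.10 instead counts missing data as relapse or heavy drinking.
- **VA records.** D.6 collects these through the final follow-up.

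**The concern.** The safety steps are not in question. The difficulty is that the rule ends study participation, where stopping CBT and contingency management (CM) would be enough. D.8.7 shows that the protocol can separate the two: it still seeks the alliance measure from people who leave treatment early. E.1.3 uses the broader term, and no available sentence keeps these people in the scheduled visits.

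For an event after randomisation, the outcomes still to come would then be missing because of the participant's clinical state. That state may well be related to drinking, so the missingness could be informative. It also arises from the protocol's own wording and not from the participant's choice, so it is avoidable.

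An imbalance between arms is conceivable. Hypothesis 1a expects that "Mobile contingency management for AUD will be associated with greater treatment engagement and treatment completion". If CM participants attend more sessions, they are asked about suicidality more often and have more occasions to trigger the rule. Better outcomes with CM could work in the opposite direction.

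**Working it through.** **What is lost, by timing of the event**

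- At screening: nothing is lost from the randomised set, because D.3 randomises at the first treatment session.
- After randomisation but before the post-treatment visit: all three post-baseline visits are lost. The Aim 1 models take outcomes at end of treatment, 6 months and 12 months, so this person has no outcome row in the ML fit. Drinking is recorded at each session (D.8.8), but those records do not enter the Aim 1 model. MI would retain the person. Its baseline predictors could include screening depression and suicidality, but not the later crisis.
- Between post-treatment and 6 months: two visits are lost, including the primary endpoint. The person stays in the ML fit through the post-treatment row.
- Between 6 and 12 months: one visit is lost, including the drinking status used for QALYs.
- At the 12-month visit: little or nothing is lost.

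**The plan's own power figures**

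Inputs from section F: 140 participants, 3 observations, ICC 0.20, and 119, 101 and 86 people remaining under 15% attrition per visit. With n people observed m times, the effective sample size (ESS) is n × m / (1 + (m − 1) × 0.20).

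- Full data: 140 × 3 / 1.4 = 300, as stated.
- With attrition, 86 people have three visits, 101 − 86 = 15 have two and 119 − 101 = 18 have one. ESS = 86 × 3 / 1.4 + 15 × 2 / 1.2 + 18 = 227.3, against 227 stated.
- Power at d = 0.43 is Φ(0.43 × √(227/4) − 1.96) = 0.900, as stated. Two-sided alpha of 0.05 is assumed, since the plan gives none.

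**Number affected and power**

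The documents give no event rate. Assume 2-5%.

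- People: 0.02 × 140 = 2.8 and 0.05 × 140 = 7, so about 3-7.
- Power, taking the plan's ESS at face value and placing these losses on top of its attrition: at 2%, ESS = 227 × 0.98 = 222.5 and power 0.894; at 5%, ESS = 227 × 0.95 = 215.7 and power 0.884.

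**Shift in the 6-month contrast**

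Let the withdrawn fractions in the two arms be w1 and w2, and let withdrawn people have D more heavy drinking days than those retained, with D the same in both arms. Leaving them out shifts the difference in means by |w1 − w2| × D. Assume 5% versus 2%, D of 5-10 days, and all events before the 6-month visit.

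- (0.05 − 0.02) × 5 = 0.15 days; (0.05 − 0.02) × 10 = 0.30 days.
- If only half the events precede the visit: 0.075-0.15 days.
- With equal rates and equal D: zero.

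For scale, d = 0.43 at an assumed SD of 8-10 days is 0.43 × 8 = 3.44 to 0.43 × 10 = 4.30 days. The shift is therefore 0.15/4.30 = 3.5% to 0.30/3.44 = 8.7% of that difference.

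A second illustration uses only the attendance mechanism: the same risk per session in both arms, with an assumed 10 sessions attended under CM and 7 under CBT alone. A CBT-arm rate r becomes 1 − (1 − r)^(10/7) under CM.

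- r = 2% gives 2.84%, a difference of 0.84 points; 0.0084 × 5 = 0.04 days.
- r = 5% gives 7.07%, a difference of 2.07 points; 0.0207 × 10 = 0.21 days.

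Both illustrations simply omit the withdrawn people and work in mean days. The planned baseline-adjusted ML and MI analyses could reduce the shift.

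**The case against.** The strongest reply is that the loss of visits is inferred. E.1.3 is a safety paragraph and does not say what withdrawal stops. It refers to a laboratory risk policy that is not included, and consent pages were removed. Staff might still follow these people up. That is fair, but the available text provides for no such follow-up, and staff applying it literally would end the visits.

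The second reply is that the analysis plan already softens the problem. Someone withdrawn after the post-treatment visit stays in the ML fit, MI keeps the rest, and the sensitivity analyses show how far results depend on the missing-data approach. This stands as mitigation. It does not supply the missing observations. The relapse rule in D.10, if used, would score a person removed by staff as drinking heavily whatever they actually drank.

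The third reply is size. The trigger is narrow, a few people are likely to be affected, and the losses may fall within the attrition already allowed for. The 86 people at 12 months come from a deliberately pessimistic scenario, and D.10 cites retention above 80% at 12 months in the team's other trials. This stands, and it is why the point is minor.

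The fourth reply is that ending participation is a cautious safety choice, and that contact after a crisis carries burden and consent questions. This also stands in part, so the remedy makes contact depend on clinical judgement and continuing consent.

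A reader might infer that data already gathered are thrown away. No text says so; only later visits are at issue. A reader might also infer that the rule biases the comparison for or against CM. The documents give no event rate and no evidence of a difference between arms, and the plausible mechanisms point both ways.

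**Conclusion.** The point holds as a minor one. Read literally, the rule ends visit-based outcome collection for people who reach imminent risk after randomisation and before the 12-month visit. Outcomes already recorded remain. VA records probably remain too, although the plan does not say whether their collection continues after withdrawal; they would inform utilisation and cost but not drinking.

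Under the assumed rates the loss of power is one to two percentage points, and the illustrated shift in the primary contrast is a fraction of a day. Every rate, gap, SD and attendance figure behind these sizes is an assumption. The sign would reverse if withdrawn people drank less than the others.

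The loss of 12-month drinking status matters for QALYs only if the cost-effectiveness analysis is run, which section F makes conditional on a significant primary outcome. D.8.1 states an interest in suicide-related phenomena, but section F has no analysis of them, so that loss is secondary. Nothing here supports the view that the rule threatens the trial's validity.

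**What to change.** Keep the risk assessment, the senior second opinion and the emergency-room escort unchanged. In E.1.3, replace withdrawal from the study with: *study treatment discontinued where clinically indicated*. Add that, unless the participant withdraws consent, the post-treatment, 6-month and 12-month assessments will be offered when clinically appropriate and VA record collection will continue. Report imminent-risk events by arm, with the number of sessions attended, so that any imbalance can be seen.

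The cost is a short protocol amendment, possibly a change to the consent wording, and a few extra, clinically cleared contacts with people after a crisis. The wording change gains less if little follow-up remains, but reporting by arm stays feasible.
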